Treatment assignment and randomization, if applicable: Patients meeting study criteria will be randomized into one of two groups, either the NF-MM or MM group on a rolling admission. Preliminary assessment after 10 subjects enrolled in the study, demonstrated that participants in the intervention (MUSE) group had higher rates of depressive symptoms than participants in the control group. In order to balance these groups, we subsequently have decided to stratify by depression scores, such that the next five enrolled participants would be placed in the MUSE group if they had lower than average (for the study) BDI scores or the control group if they had higher than average (for the study) BDI scores. After these five subjects were enrolled, we will recalculate average BDI scores and decide whether to continue to stratify by depression scores or not.

Additionally, we have decided to add a no-treatment control group of 10 subjects. These individuals will be recruited after the first 20 subjects complete the trial. Thus, 30 subjects in total will now be part of this study.

Study Procedures

Study Site: Pre- and post-treatment assessments will be performed in outpatient offices at SRH in Charlestown or Cambridge (for those enrolled in the SRH study). MUSE training session will occur during the pre-treatment assessment session for the intervention groups. This training will last approximately 30 minutes and include a MM session with or without auditory NF.

Participants will then perform their 6 weeks of NF-MM with MUSE or MM without MUSE at their homes. Study staff will also call participants on a weekly basis, to remind patients to practice and provide technical support. A post-treatment assessment session will take place within one week of completion of the intervention. Those in the no-treatment control group, will simply undergo pre- and post-neuropsychological testing 6 weeks apart and receive meditation and MUSE training at their final 6-week visit.

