- 4) Qualitative assessment: Both NF-MM and MM groups will undergo a very brief qualitative interview at their post-treatment session to inquire on their subjective experience with MM with or without NF. The MM will then receive a MUSE device and practice NF-MM for two additional weeks, after which point they will receive a phone call with further questioning regarding their experience with MM with or without NF.

Biostatistical Analysis

First, we will power this study using the effect size that we calculate from the cognitive MUSE data collected by Bhayee et al. Then, we will compare our NF-MM, MM, and no-treatment control groups. We will contrast the three groups' cognitive outcomes in trail-making, symbol-digit coding, WAIS-IV digit spans. We will then compare affective outcomes using the Beck Anxiety Inventory, Beck Depression Inventory and Neurobehavioral Symptom Inventory. Finally we will compare mindfulness data from the Cognitive and Affective Mindfulness Scale. The continuous variables from the cognitive and affective measures will be analyzed with linear regression. The statistical contribution of demographic variables will be assessed using mixed effects models. We plan to perform post-hoc analysis for multiple comparisons.

Risks and Discomforts

Complications of procedures: We do not anticipate significant adverse effects from the use of MUSE technology, as it is already in wide use in the general population without reports of any significant harm. However, other neurofeedback studies have documented patient complaints of fatigue, feeling "spacey," anxiety, irritability, headache, or difficulty falling asleep (Hammond et al. 2011). Subjects will be able to contact study staff during daytime hours with questions or concerns regarding the possibility of such adverse effects. If these symptoms are believed to be stemming directly from use of MUSE and are intolerable for patients, they will be instructed to discontinue participation in the study.

Device complications/malfunctions: While it is not expected, it is possible for the MUSE device to malfunction. Participants will be able to email or call with tech support questions during standard business hours. Study staff members will call patients back to troubleshoot. While

equipment malfunction could interfere with data collection, it will not put patients at any risk of harm.

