Psychological non medical risk: Meditation practice has very infrequent adverse effects. However in patients with severe mental illness (severe depression, suicidality, disabling anxiety, tendency toward dissociation), spending time silent, alone with one's thought in a repetitive practice can rarely exacerbate psychopathology. These patients will be carefully screened and excluded from participating in the study. If MM is stirring up unpleasant thoughts and feelings, they will be able to reach study staff members during business hours, and if necessary will be discontinued from the study. Participants in this study will also be asked to fill out the BDI-II form during pre- and post-test visits. A contingency plan is in place if participants exhibit suicidal ideation. Please see the attached document.

Disclosure of Confidential Information: All patient information will be kept confidential in this study and will not be shared outside of study collaborators. Subjects' data that is collected via MUSE will also be safeguarded. Please see the attached data handling form from MUSE. Importantly, subjects data that is stored on MUSE does not include personal health information. It includes the participant's username, email, frequency of MM training, and EEG waves during meditation. Users' accounts are also password protected.

Minimization of Risks: Risks of loss of privacy will remain as with any study. For this reason, all data collected from participants will be kept in a secure, password protected database. Trackable correspondence with participants, ie email, will be conducted through a secure exchanger. Participants' data will be de-identified at the onset of the study and assigned a subject number that will be used to keep track of their study data. A key linking patient's names and their study number will only be available to key research personnel. All study data will be stored in a secure location, maintained either electronically on a password protected computer or if on paper, in a locked cabinet in a private office or office requiring a security badge to enter. Printed computer data that is no longer needed for research purposes will be properly disposed of in secure, confidential medical paperwork waste bins.

Potential Benefits

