Potential benefits to participants: Based on the mindfulness meditation literature, participation in the NF-MM or MM arms of this study is likely to have a positive impact on a patient's mood, anxiety, and biological stress levels. It may also help with attentional impairment. Individuals in the no-treatment control group will continue with care as usual. They are not expected to benefit directly from participation in this study.

All participants in all groups will receive a Muse device in compensation for completing the study.

Potential benefits to society (e.g., increased understanding of disease processes): Information from this study could potentially be useful to mTBI patients on a population level. If NF-MM is shown to significantly outperform standard MM in terms of psychological and cognitive performance, mTBI patients and their clinicians may want to consider using MUSE following brain injury. If NF does not enhance participants' practice of MM, mTBI patients and their clinicians will want to recommend against the use of the device, as its cost does not bear out in improved outcomes. If the NF-MM or MM groups outperform the no-treatment control group, results will suggest that various types of meditation interventions may be useful for affective or cognitive symptoms in individuals with traumatic brain injury.

Monitoring and QA

Independent monitoring of source data: Study staff, physicians or psychologists, will be responsible for reviewing the accuracy and completeness of form entries, case documents, and informed consent.

Safety and outcomes monitoring: Safety and efficacy data will be reviewed on a weekly basis through email or phone correspondence between participants and either a physician or psychologist study staff member. If the practice of meditation or use of neurofeedback is causing significant psychological distress or physical discomfort, the patient will be advised to discontinue participation.

Adverse event reporting guidelines: All reports of adverse psychological and physical effects will be relayed directly to the study PI and to MUSE.

References:

<http://doi.org/10.1016/j.psychres.2013.09.002>

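### The device is compensation for an undefined study completion, while serious symptoms lead to study exit with no post-test described; this may discourage reporting and makes data loss depend on harm

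*Combined protocol and SAP*

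**What the plan says.** **Compensation.** Under Potential Benefits (Potential benefits to participants): "All participants in all groups will receive a Muse device in compensation for completing the study". The protocol does not say what counts as completing, and is silent on part compensation, on participants who stop early and on return of the device.

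**Leaving the study.** Three passages deal with harm:
- Risks and Discomforts, Complications of procedures: "If these symptoms are believed to be stemming directly from use of MUSE and are intolerable for patients", then "they will be instructed to discontinue participation in the study".
- Risks and Discomforts, Psychological non medical risk: participants in whom meditation stirs up unpleasant thoughts and feelings can reach staff and "if necessary will be discontinued from the study".
- Monitoring and QA, Safety and outcomes monitoring: where meditation or neurofeedback causes marked distress or discomfort, "the patient will be advised to discontinue participation".

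**Post-test.** Study Procedures, Study Site: "A post-treatment assessment session will take place within one week of completion of the intervention". No assessment is described for a meditation-arm participant who stops before then.

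**Access to the device.** Study Site: "Participants will then perform their 6 weeks of NF-MM with MUSE or MM without MUSE at their homes". Data to be collected, item 4, places the MM group's device after the post-treatment interview: "The MM will then receive a MUSE device and practice NF-MM for two additional weeks", followed by a phone call.

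**The concern.** Each provision is unremarkable alone. The difficulty is how they combine. A participant who reports a symptom serious enough to meet an exit threshold is directed out of the study as a whole, not merely off the practice. If compensation requires completing the study, that report may cost the device. Safety information between visits comes from weekly phone or email contact, so it depends on what participants choose to say.

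Two things are at stake. First, the more serious harms may be under-reported, and some participants may carry on practising with symptoms. Second, those who do report and leave have no planned post-test, so outcome data go missing for a reason connected with how the participant fared. Anxiety is both a complaint that the protocol lists for neurofeedback and the construct that the BAI measures. The Biostatistical Analysis section does not say how missing outcomes will be handled.

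**Working it through.** The plan states no figure on this point: no dropout rate, harm rate, alpha, power or standard deviation. The check is therefore mainly a reading of the provisions together, followed by an illustration of scale.

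**Step 1: follow one participant through the text.** An NF-MM participant develops symptoms in week 3 that are intolerable and attributed to MUSE.
- Complications of procedures directs that participant out of the study.
- Study Site times the post-test from completion of the intervention, so no visit is described for this person.
- The compensation sentence attaches the device to completing the study, which this person, on a plain reading, has not done.

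An MM participant with marked distress from meditation follows the same path through the psychological-risk and monitoring passages, although there the exit is conditional or advisory. A no-treatment participant has no practice to stop during the six weeks, so the path does not apply.

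**Step 2: test whether completing could be read another way.** The MM group receives its device after the post-treatment interview but before two further weeks of NF-MM and a final call. For that group, the device arrives before the last study contact. The protocol therefore leaves open whether completing means finishing the practice, attending the post-test or finishing all contacts.

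**Step 3: sample size.** Treatment assignment and randomization gives 20 participants before the no-treatment group, 10 in that group and 30 in total: 20 + 10 = 30, which agrees. No allocation ratio is stated for the 20; about 10 per meditation arm is assumed below.

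**Step 4: scale, under stated assumptions.**

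*Share of an arm.* One participant in 10 is 1/10 = 10%. If 2 of 10 have exit-level symptoms and one stays silent, the observed rate is 1/10 = 10% instead of 2/10 = 20%.

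*Chance of seeing no report in an arm of 10.* With true rate p and probability r that a case is reported, this is (1 − p·r)^10. The values of p and r are assumptions.

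| True rate p | All reported (r = 1) | Half reported (r = 0.5) |
|---|---|---|
| 0.1 | 35% | 60% |
| 0.2 | 11% | 35% |
| 0.3 | 3% | 20% |

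*Shift in the completer mean.* If k of 10 are lost and would have scored m SD worse than those kept, the completer mean is too favourable by (k/10)·m. For k = 1, m = 0.5 this is 0.05 SD; for k = 2, m = 1.0 it is 0.20 SD; for k = 3, m = 1.5 it is 0.45 SD.

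*Loss of precision.* With two-sided alpha 0.05, 80% power and a normal approximation (all assumed), the detectable difference is (1.96 + 0.84)·sqrt(1/n1 + 1/n2): 1.25 SD at 10 v 10, 1.29 at 10 v 9, 1.33 at 10 v 8 and 1.38 at 10 v 7. Precision suffers little; selective loss is the more important effect.

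**The case against.** The strongest reply is that the protocol nowhere says an early stopper goes without a device. Completion is undefined, and the consent form, which is not in the public text, may hold fuller terms. A reader might infer that the device goes only to those who finish. The text does not say so, and the point should not be put that strongly. What remains is that the protocol's own sentence, read plainly with the exit passages, allows that inference and contains nothing to dispel it.

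A reader might also infer that reporting any harm is penalised. That is not supported. For MUSE symptoms, exit requires that they be both intolerable and attributed to the device; the other passages apply to marked distress or discomfort, or only where necessary. Lesser symptoms carry no stated loss. Moreover, someone who finds MUSE intolerable may not much want one, which weakens the motive in that case. This limits the incentive to the more serious reports, but those are the reports that safety monitoring most needs.

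Third, staff call weekly, and a physician or psychologist reviews safety every week. Participants who stay silent and finish still give BAI, BDI-II and NSI scores, so some worsening would show. These are partial safeguards: the weekly contact still rests on self-report.

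Fourth, it is tempting to say that the compensation rule is why early stoppers would not return. The main cause lies elsewhere: they are directed out of the study and no visit is described for them. Compensation at most adds to this. The objection stands, and it means that rewording the compensation sentence alone would not recover the data.

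Finally, the no-treatment group should be left out of any claim about concealment, since it has no intervention harm to conceal during the six weeks.

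**Conclusion.** The concern holds in a limited form. For participants in the two meditation arms, a report serious enough to trigger exit may cost the compensation and leaves no planned outcome assessment. This may discourage such reports, and it ties missing outcome data to harm. The conclusion rests on a plain reading of completing the study, on the absence of any described visit for early stoppers, and on weekly contact being self-report.

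The size is unknown. At an assumed 10 or so per arm, each affected participant is about 10% of the arm's harm or outcome data; the other figures in the working only show what assumed rates would imply. If no participant reaches an exit threshold, there is no effect on the data. The documents do not support a direction or size for any difference between the NF-MM and MM arms. The case for acting is that the change is cheap and protects both harm reporting and retention, not that bias has been shown.

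**What to change.** 1. Under Potential benefits to participants, replace the compensation sentence with a rule that the device goes to every participant, in all three groups, who attends the six-week assessment, whether or not they continued the practice and whatever symptoms they reported.
2. Under Study Site, state that participants who stop the practice early are still invited to that assessment at six weeks, if they agree.
3. Put matching wording in the consent form, so that participants know that reporting symptoms or stopping practice does not affect compensation.
4. Reconcile the three passages on stopping, which variously instruct, discontinue if necessary and advise, with each other and with item 2. No view is taken here on which clinical rule is right.

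Leave the NF-MM group's home use and the MM group's two-week device period as they are; both are study procedures. Giving a device to every enrolled participant regardless of attendance is not recommended, since it would remove the incentive to return for the post-test.

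The cost is a few sentences in the protocol and consent form, a few extra devices and some extra post-test visits.
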